### 5 Definitions

**Study Drug.** Study drug in this study is ABX464.

**Baseline.** Baseline is defined by patient and by variable as the last non-missing value before the first dose of study drug.

**Study Day.** Study day is the number of days since start of treatment where the date of first dose is counted as Day 1.

**Protocol Deviation:** a deviation related to study inclusion or exclusion criteria, conduct of the trial, patient management or patient assessment. This refers to any change, divergence, or departure from the study design or procedures defined in the protocol.

**Major Protocol Deviation:** These are defined as protocol deviations that are liable to bias the evaluation of the main study endpoints. The following deviations will be considered as major (non-exhaustive list):

- Non-compliance with the inclusion or exclusion criteria;
- Non-compliance with the study treatment
- Intake of prohibited medication;

**Non-compliance with time window** The actual major protocol violations are identified by the study team and documented in an Excell file.

## 6 Analysis DatasetsSafety dataset (SAF population)

The Safety dataset (SAF population) is defined as those subjects included in the study, who have received at least one dose of the study treatment.

### 6.1 Full Analysis dataset (FAS population)

The Full Analysis dataset (FAS population) is defined as those subjects included in the study, who have received at least one dose of the study treatment, and who have at least baseline data.

### 6.2 Per Protocol dataset (PP population)

The Per Protocol dataset (PP population) is defined as those subjects of the FAS population without any major protocol deviation.

## 7 Safety Monitoring

No safety monitoring reports are planned.

A Data Safety Monitoring Board with expertise and experience in the management in HIV will review the safety of the trial, every 4 patients are recruited, in order to recommend, if appropriate, the continuation of the study.

## 8 Interim Analysis

An interim analysis have been produced when the first 12 HIV-positive subjects (Cohort 1) reached day 56 of follow-up. The interim analysis includes the following data:

- Safety and clinical parameters;
- HIV-1 RNA, CD4+ and CD8+ counts;
- Hematology and biochemistry parameters;
- Pharmacokinetic parameters in plasma, PBMCs and rectal tissue;
- Total HIV-1 DNA reservoir in PBMC and rectal tissue.

## 9 Data

## 10 Statistical Methods

### 10.1 General Principles

All statistical methods will be based on the International Conference on Harmonisation (ICH) E9 document "Statistical Principles for Clinical Trials".

Data will be summarised by cohort. A total column showing all patients will be included for baseline and safety summaries. Where appropriate, data will also be summarised by visit with summaries for each visit attended as scheduled and an additional summary for final (last scheduled visit or early withdrawal). The format of the summaries is defined in the shells in a separate document.

All summary tables will be made up of the following three columns:

- Cohort 1: Hiv infected subjects receiving the 150mg dose of ABX464 for 28 days;
- Cohort 2: Hiv uninfected subjects receiving the 50mg dose of ABX464 for 28 days;
- Cohort 3: Hiv infected subjects receiving the 50mg dose of ABX464 for 84 days.

In addition, summary tables for total DNA will be made up with an additional column of cohort 1 and Cohort 3 pooled.

In summary and analysis tables of continuous variables, standard descriptive statistics (N, mean, standard deviation [SD], median, quartiles, minimum, maximum ) will be presented when relevant. 95% confidence Intervals (CI) will be presented in the statistical analysis outputs as appropriate. For PK summaries, arithmetic mean (AM), geometric mean (GM) and coefficient of variation (%CV) will be used to summarise the data. The minimum and maximum statistics will be presented in summary tables to the same number of significant figures as the original data. The mean/AM, median, GM, CI, SD and will be presented to one more significant than the original data.

For numeric data which includes non-numeric values (e.g. PK data reported as BLQ or lab results reported as < 10 or >100) the following principles will be applied when summarising the data:

- BLQ will be replaced with a value that is ½ of the lower limit of quantification (LLQ)
- Results reported as < x will be treated in the same way as BLQ with LLQ=x
- Otherwise AM, GM, SD, CI and %CV will not be calculated
- Whenever meaningful, minimum, median and maximum will be presented based on the reported data (e.g. minimum = <10, median = 20, maximum = >100)

In summary tables of categorical variables, the number of non-missing observations by category will be presented with percentages. The number of missing observations will also be presented when the count is non-zero. Unless otherwise specified, the denominator for each percentage will be the number of non-missing observations within the column. All percentages will be presented to one decimal place.

If changes in severity for the same TEAE have been reported separately but with the same AE number, they will be collapsed to a single AE with maximum severity for the summary tables, but listed as reported.

Classifications of medical history, concomitant medication and adverse events will be sorted alphabetically within the summary tables.

If any laboratory assessments are repeated at the same visit, the result from the repeat assessment will be used in summaries. Both values will be listed.

Data collected on the eCRF will be presented within data listings. The data listings will be sorted by treatment group, country, centre number, patient number and visit/week/day. Treatment group will be as treated. If any patients receive the wrong treatment this will be flagged in all listings. Visits outside the visit windows will be identified within the listings.

The date format for all output presentations will be 'ddMMMyyyy'.

All statistical analysis will be performed using SAS 9.3 or higher.

If any of the assumptions underlying the formal statistical methods proposed are violated during the analysis of the final data, alternative statistical methods will be used and any changes documented in the statistical methods section of the clinical study report (CSR), including the rationale for use.

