9.3. Safety Analyses

Adverse events will be coded using the standard dictionary (MedDRA) down to the lower level term (LLT).

An overall summary table will be presented: any adverse event, any treatment emergent adverse event (TEAE), any serious adverse event (SAE), death, any grade 3 or higher adverse events from baseline to EoS.

Two periods will be defined for TEAE:

- Any adverse event which occurs or worsens from first dosing to Day 28;
- Any adverse event which occurs after Day 28.

Adverse events will be described by primary system organ class and preferred term. Numbers and percentage of subjects, and number of occurrence of adverse event will be presented for:

- TEAE;
- Serious TEAE;
- TEAE leading to drug discontinuation;
- TEAE of grade 3 or 4;
- TEAE for which relationship with the study drug is recorded as possible or probable.

The assessment of safety will be based on the frequency of adverse events (with and without regard to causality) graded according to the Division of AIDS table for grading the severity of adult and pediatric adverse events (version 2.0, November 2014) and also, the review of individual values for clinical laboratory data, vital signs and ECG focusing on the detection of abnormal values and PCSAs [potentially clinically significant abnormalities (PCSA) determined upon investigator considerations].

Adverse events will be tabulated (counts and percents) by group. All adverse events will be listed and the data will be tabulated by body system/organ class. Adverse event tabulations will include all treatment emergent adverse events, which will be further classified by severity, and relationship to treatment and dose level.

Clinical laboratory parameters, vital signs, ECG will be summarized by using descriptive statistics (n, mean, SD, SEM, median, minimum and maximum). Number of subjects with at least one abnormal values will be tabulated (counts and percents) for each parameter in summary shift tables, by group and dose.

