#### 4.4 Safety endpoint

Analysis of safety will be performed on the safety data set consisting in all subjects who received at least one dose of ABX464 in the study. The assessment of safety will be based on the frequency of adverse events (with and without regard to causality) graded according to the Division of AIDS table for grading the severity of adult and pediatric adverse events (Version 2.0 November 2014) and also, the review of individual values for clinical laboratory data, vital signs and ECG focusing on the detection of abnormal values and PCSAs [potentially clinically significant abnormalities (PCSA) determined upon investigator considerations].

Adverse events will be tabulated (counts and percents) by group and dose. All adverse events will be listed and the data will be tabulated by body system/organ class. Adverse event tabulations will include all treatment emergent adverse events, which will be further classified by severity, and relationship to treatment and dose level.

Clinical laboratory parameters, vital signs, ECG will be summarized by using descriptive statistics (n, mean, SD, SEM, median, minimum and maximum). Number of subjects with at least one abnormal values will be tabulated (counts and percents) for each parameter in summary shift tables, by group and dose.

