#### 11.4.2 Laboratory Data

Routine clinical laboratory results will be carried out at screening, all visits during the treatment period. The laboratory parameters include:

- Haematology: hemoglobin, hematocrit, WBC, neutrophils, lymphocytes, monocytes, eosinophils, basophils, platelet count, INR, PT
- Biochemistry: sodium, potassium, chloride, calcium, phosphate, glucose, BUN or urea, creatinine, AST, ALT, alkaline phosphatase, total bilirubin, GLDH, total protein, lipase, albumin, LDH, gGT, CRP,

Laboratory parameters will be summarised at each visit using descriptive statistics on the SAF set. Laboratory parameters classified as normal/ abnormal non clinically significant (NCS)/ abnormal clinically significant (CS) will be presented in a shift table showing changes from baseline to each visit for patients with at least one abnormal CS value. Baseline is defined as the last non-missing value before the first dose of study drug, which is Day 0.

If laboratory results are repeated at the same visit, the repeated result will be used in summaries (instead of the original one) provided the sample was taken within the visit window, otherwise the original result will be used. All results will be listed.

Laboratory results at unscheduled visits will be included in the listings but will not be summarised.

For all female patients of childbearing potential, a blood pregnancy test ( $\beta$ -HCG) will be performed at Day 0 and then a urine pregnancy test will be performed at each visit until VR. Results of all pregnancy testing will be listed only.

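### SAP 10.1 and 11.4.2 conflict on repeat laboratory tests, and with no worst-value table, transient or unscheduled abnormalities drop out of the laboratory summaries

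*SAP*

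**What the plan says.** Two SAP sections set a rule for repeat tests. Section 10.1 has no timing condition: "If any laboratory assessments are repeated at the same visit, the result from the repeat assessment will be used in summaries", followed by "Both values will be listed". Section 11.4.2 adds a condition: "the repeated result will be used in summaries (instead of the original one) provided the sample was taken within the visit window"; if the repeat is outside the window, the original stands.

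On tests outside the planned visits, SAP 11.4.2 says: "Laboratory results at unscheduled visits will be included in the listings but will not be summarised".

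The laboratory shift table in SAP 11.4.2 uses the classes normal, abnormal not clinically significant and abnormal clinically significant (CS). It "will be presented in a shift table showing changes from baseline to each visit for patients with at least one abnormal CS value". SAP 4.4 promises a second output: "Number of subjects with at least one abnormal values will be tabulated (counts and percents) for each parameter in summary shift tables". It does not say whether replaced or unscheduled values count.

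Protocol 9.3 bases safety on adverse event frequency and on a review of individual laboratory, vital-sign and ECG values, "focusing on the detection of abnormal values and PCSAs".

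**The concern.** A programmer cannot follow both repeat rules when the repeat falls outside the window. Whichever rule is used, an abnormal first value followed by a normal in-window repeat is summarised as normal. A value from an unscheduled visit is not summarised at all. Both rules act on the values that a search for abnormalities most needs.

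At stake is how well the laboratory tables of a small Phase Ib study reflect what was measured. With 12 subjects per cohort, one subject more or less changes how a row reads.

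**Working it through.** The documents state no figure on this point, so the check is mainly a comparison of text.

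**1. What each rule puts in the laboratory summaries**

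| Situation | SAP 10.1 | SAP 11.4.2 |
|---|---|---|
| First value abnormal, repeat normal and in window | repeat (normal) | repeat (normal) |
| First value abnormal, repeat normal and out of window | repeat (normal) | original (abnormal) |
| First value normal, repeat abnormal and in window | repeat (abnormal) | repeat (abnormal) |
| Abnormal only at an unscheduled visit | not addressed | not summarised |

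Row 2 is the conflict. Rows 1 and 4 are the loss. Row 3 shows that the rule can also add an abnormality, so its net direction depends on why tests are repeated, which the documents do not say.

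**2. Whether another laboratory table recovers the value**

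The shift table goes visit by visit. The additional final summary in SAP 10.1 covers the last planned visit or withdrawal, not the peak. Protocol 9.3.1 also ties its descriptive statistics to scheduled assessments. No worst-post-baseline or by-grade laboratory table is described. The SAP 4.4 count is placed inside the summary shift tables, so it most naturally inherits the same exclusions, but the text does not settle this.

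The SAP 11.4.2 shift table is limited to patients with at least one CS value. A subject with only non-CS abnormalities is therefore outside it in any case, and the SAP 4.4 count is the table in which that subject should appear.

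**3. Which results are unscheduled**

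- *Cohort 1.* The visit table in SAP 3.4 and protocol 5.3 give no visit between Day 1 and Day 28. Any laboratory result in that interval is unscheduled and unsummarised.
- *Cohort 2.* There are visits on Days 7, 14 and 21. Protocol 5.3.3 lists no hematology or biochemistry at them, and Table 5 has no row for them. The HIV-negative column of Table 5 sums to 19.2 + 124 + 132.5 + 20 + 48.5 = 344.2 mL at the low end and 19.2 + 126.7 + 135.2 + 22.7 + 51.2 = 355.0 mL at the high end. The printed total is 345.2 to 354.0 mL. Three further draws of 5 + 3 = 8 mL (24 mL) are not in it. Against this, protocol 5.4.3 asks for the laboratory parameters at every visit, and SAP 11.4.2 refers to all visits in the treatment period. The flow chart in protocol 5.1 could not be read reliably enough in the text available to settle the matter.

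**4. Weight of one subject**

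1/12 = 8.3 percentage points of a cohort; 1/36 = 2.8 points of the total column.

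**5. Illustration under assumed inputs**

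Let p be the chance that a subject's first value is abnormal and is then repeated in window, and q the chance that the repeat is still abnormal. The chance that a 12-subject cohort shows at least one abnormal subject is 1 − (1 − p)^12 if the worst value counts, and 1 − (1 − pq)^12 under the repeat rule.

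| p | q | worst value counts | repeat rule |
|---|---|---|---|
| 0.05 | 0.5 | 46% | 26% |
| 0.10 | 0.5 | 72% | 46% |
| 0.10 | 0.8 | 72% | 63% |
| 0.20 | 0.5 | 93% | 72% |
| 0.30 | 0.5 | 99% | 86% |

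At q = 1 the two agree; at q = 0 the repeat rule shows nothing. Neither p nor q is in the documents, so the table shows sensitivity and is not an estimate.

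**The case against.** The strongest reply is that nothing is hidden. All values are listed. Individual values are reviewed, and the protocol's phrase about detecting abnormal values describes that review. Under protocol 8.3.1, laboratory findings judged clinically significant are recorded as adverse events, with no exception for repeated or unscheduled samples, and SAP 11.4.1 tabulates treatment-emergent events. This stands. A reader might infer that these abnormalities vanish from the safety tables altogether; the documents do not support that. Findings prompted by symptoms are among those most likely to be recorded as adverse events.

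A repeat may also follow a spoiled sample, and then using it is sensible. That stands too, and it is a reason to leave the by-visit statistics alone.

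It can be argued that the specific rule in 11.4.2 simply qualifies the general one in 10.1. That is a reasonable reading, but the SAP states no order of precedence.

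Three other stronger readings also fail:

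- *A large fixed share is lost.* In a bivariate normal model, a first value above the 97.5th percentile is followed by a second one above it with probability 18%, 33% or 59% at assumed correlations of 0.5, 0.7 or 0.9. This invites the claim that 41 to 82% of first abnormal values are lost. The claim requires every such value to be repeated in window. If 20% were repeated the range would be 8 to 16%; if 50%, 20 to 41%. The model also contains only noise around a limit, where a normal repeat may be the better measurement, so it does not measure missed toxicity.
- *No planned laboratory data before Day 28 in either 28-day cohort.* This is secure for Cohort 1 only, because the passages on Cohort 2 disagree.
- *Dose selection is distorted.* The study has two dose levels, but its primary objective is drug distribution and no dose-selection rule is stated.

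The table shells are a separate document and might settle the SAP 4.4 count.

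**Conclusion.** The concern holds for the laboratory tables. The repeat rules in SAP 10.1 and 11.4.2 conflict for out-of-window repeats. As written, a value that normalises on an in-window repeat, or is found only at an unscheduled visit, is absent from the laboratory summary and shift tables. It is probably also absent from the SAP 4.4 count; that part rests on reading the count as subject to the same rules. Because CS findings have the adverse event route, the loss falls mainly on abnormalities not judged clinically significant, which otherwise reach only the listings and the individual review.

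Each subject missed costs 8.3 percentage points of a cohort. The overall share missed cannot be stated without a repeat frequency. This is a cheap improvement to a descriptive analysis and not an error of calculation.

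**What to change.** 1. Keep the by-visit descriptive statistics as planned.
2. Add a shift table from baseline to each subject's worst post-baseline value per parameter, for the whole safety set, not only patients with a CS value.
3. State that the SAP 4.4 count uses all post-baseline values (original, repeat and unscheduled), with documented sample errors flagged or excluded.
4. Write one repeat rule, in the same words, in SAP 10.1 and 11.4.2.
5. Reconcile protocol 5.3.3 and Table 5 with protocol 5.4.3 and SAP 11.4.2 on laboratory tests at Cohort 2's Days 7, 14 and 21, so that it is clear which results are scheduled.

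The cost is SAP wording, one derived variable and one extra table, from values that are already to be listed. The downside is slightly higher abnormality counts, some of which may be spurious.

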## 10.2 Missing Data

There will be no imputation of missing data in this study.

# 11 Statistical Output

General principles for layout of the statistical output are described in Section 10.1, including specification of the table columns, and these are illustrated for each unique table in the table shells (separate document). For clarity and brevity in this document the phrase “by treatment group” or “by study cohort” is understood for all summaries and is not included within the text of this section.

The study analysis will be performed following database lock upon the completion of the last patient or upon its early discontinuation whichever occurs first.

## 11.1 Patient Disposition

A patient is considered to be a baseline failure if the patient signs the informed consent but withdraws before the screening visit. Reasons for exclusion will be recorded for patients who do not enter the study and presented in a data listing.

A summary of the number of screened patients, baseline failures, screening failures and reasons for screening failure will be produced for all enrolled patients.

The number (%) of patients who complete or withdraw from the study and the main reason for withdrawal will be summarised for all randomised patients.

The patient disposition table will summarise the following data for all randomised patients:

- The number (%) of patients in the FAS
- The number (%) of patients in the SAF
- The number (%) of patients in the PP set

A data listing presenting the eligibility for the analysis sets for each patient will also be presented.

Protocol deviations will be reviewed and classed as major or minor during the blind DRM. A listing of all patients with protocol deviations will be presented.

## 11.2 Patient Characteristics at Baseline

### 11.2.1 Demographic and Baseline Characteristics

Age will be calculated using Date of Birth (DOB) and date of informed consent and presented as age at last birthday as an integer.

BMI is the patient’s body weight in kilograms divided by the square of the patient’s height in metres.

Age, gender, race, height, weight and BMI will be summarised.

#### 11.2.2 Medical History and Current Medical Conditions

All conditions will be coded using the version of the Medical Dictionary for regulatory Activities (MedDRA). Past medical/surgical history (conditions that stopped prior to or at the screening visit) and current medical conditions (classified as 'ongoing') will be summarised by system organ class (SOC) and preferred term (PT). The number (%) of patients reporting each condition will be presented.

#### 11.2.3 Procedures / Non-Drug Therapies

All procedures/non-drug therapies recorded on the CRF will be listed only.

### 11.3 Analysis of Endpoints

The main analysis set for PK and efficacy analyses will be the FAS, and the primary analysis will be repeated for the PP Set if applicable.

Safety endpoints will be summarized on the SAF dataset

#### 11.3.1 Analysis of the primary endpoint

The primary endpoint (Main pharmacokinetic parameters ( $C_{max}$ , AUC) after first dose of ABX464 (Day 1) and for

- ② Cohort 1: at Day 28 and at Day 56 for plasma, PBMC and rectal tissue.
- ② Cohort 2: at Day 28 and at Day 56 for plasma and PBMC. Rectal tissue only at Day 28.
- ② Cohort 3: at Day 28, Day 84 and Day 112 for plasma, PBMC and rectal tissue.

will be descriptively summarised on the FAS set.

The primary endpoint analysis will be repeated for the PP set if applicable.

#### 11.3.2 Analysis of secondary endpoints

##### 11.3.2.1 Number and grade of treatment-emergent adverse events

Number and grade of treatment-emergent adverse events, including treatment-emergent serious adverse events, adverse events leading to investigational product discontinuation, during the study.

Treatment-emergent adverse events will be summarized on the SAF dataset. Definition of treatment emergent AEs are found in General Safety Analysis Section (Section 14.4.1).

